8.1.2 Hematological toxicity

A hematological toxicity management plan will be implemented if any of the following criteria are met:

- Hemoglobin < 7.0 g/dL for men, <6.5 g/dL for women
- Platelets <50,000/mm³
- Absolute neutrophil count <600/mm³

Management plan:

1. Discontinue linezolid

- 2. Assess for use of other myelosuppressive medications and discontinue non-essential medications (e.g., co-trimoxazole)
- Repeat blood count will be performed every 2 (+/-1) days until stable. If the abnormal hematological parameter(s) returns to Grade <2 and any associated symptoms resolve, linezolid 1200 mg can be restarted.
- 4. Continue to follow blood count every 2 (+/-1) days until stable. If after restarting linezolid, the abnormal hematological parameter returns to the above criteria, linezolid should again be discontinued.
- 5. Continue to follow blood count every 2 (+/-1) days until stable. If the abnormal hematololgical parameter(s) returns to Grade <2 and any associated symptoms resolve, linezolid can be restarted at 600 mg daily.
- 6. Continue to follow blood count every 2 (+/-1) days until stable. If after restarting linezolid, the abnormal hematological parameter returns to the above criteria, linezolid should be discontinued permanently.

8.1.3 Gastrointestinal toxicity

Study treatment will be stopped for any Grade 3 or higher gastrointestinal adverse events, including nausea, vomiting, diarrhea, or loss of appetite with weight loss. If a participant develops Grade 3 or 4 GI symptoms, rifampicin will be discontinued first until symptoms have resolved to Grade ≤ 2 , at which point it can be reintroduced. If GI symptoms do not improve after discontinuing rifampicin, linezolid will be discontinued until symptoms have resolved to Grade ≤ 2 , at which point it can be reintroduced.

8.1.4 Neurotoxicity

Mild to moderate headache is an expected adverse reaction linezolid, whereas peripheral neuropathy and optic neuropathy are expected to be relatively uncommon over a 4-week treatment period. Study treatment will be stopped for any Grade 3 or higher neurologic adverse events, including neuropathy or visual changes. If participants develop signs/symptoms of optic neuropathy, we will endeavor to have them evaluated by an ophthalmologist in Masaka if safe and logistically feasible. If a participant develops Grade 3 or higher symptoms, linezolid will be discontinued for up to 14 days until symptoms have resolved to Grade ≤ 2 , at which point linezolid 1200 mg can be reintroduced.

8.1.5 Rash

Mild to moderate rash is a potential adverse reaction to rifampicin or linezolid. Participants with a Grade 1 or 2 rash may continue study medications at the site investigator's discretion. The participant should be advised to contact the site investigator immediately if there is any worsening of the rash, if any systemic signs or symptoms worsen, or if mucosal involvement develops. Study treatment should be discontinued in participants who develop Grade 3 or higher rash. Participants will be followed off study treatment, on study. Participants should be treated as clinically appropriate and followed until resolution of the AE. If the etiology of the rash can be definitely diagnosed as being unrelated to study medications and due to a specific medical event or a concomitant non-study medication, routine management should be performed and documentation of the diagnosis provided.

8.1.6 Other toxicities

Grade 2 toxicities: For grade 2 toxicities, the participant will be followed more carefully, with additional laboratory and/or clinic visits as necessary, and the study drugs temporarily held at the investigator's discretion.

Grade 3 toxicities: For any grade 3 toxicity that, in the investigator's judgment is due to rifampicin or linezolid, the causative drug should be held. The clinician should rule out other possible causes of the symptoms before discontinuing study medication. When possible, concomitant medications should be held first at the discretion of the investigator if he/she suspects they are contributing to the toxicity. Depending on the nature and severity of the toxicity, the degree to which it resolves, and/or the emergence of alternative explanations for the toxicity or the subject's deterioration, the study drugs(s) may be restarted at the discretion of the investigator.

Grade 4 toxicities: Any participant with grade 4 renal, hepatic, cardiac, hematological, or neurologic toxicity will be immediately discontinued from study therapy. The laboratory test or clinical finding in question will be reassessed as soon as possible. The repeat test will guide management of the event as follows:

- 1. If the repeat assessment shows toxicity of grade 3 or lower, and if the participant has continued to receive study drugs between the two testing dates, then the participant will be managed according to the appropriate toxicity level of the repeat test.
- 2. If the repeat test shows toxicity of grade 3 or lower, and if the participant has not received study drugs between the two testing dates, then the participant will be managed at the discretion of the investigator with regard to the re-administration of study drugs, and otherwise according to the toxicity level of the repeat test.
- 3. If the repeat test shows grade 4 toxicity, then the participant will be permanently discontinued from study medications unless a clear alternative cause for the toxicity has been identified, in which case, re-administration of study drugs may be considered but only with prior approval from the PI and site PI. Further treatment of TB will be directed by the investigator and treating clinician on an individualized basis. The participant will continue to be followed for study monitoring purposes (as are other participants who make a permanent departure).

For other grade 4 toxicities, the study drugs will be temporarily held and may be restarted or permanently stopped at the discretion of the investigator. For all toxicities that are treatment-emergent and that require the study therapy to be temporarily or permanently discontinued, relevant clinical and laboratory tests will be obtained as clinically indicated and repeated as needed until final resolution or stabilization of the toxicity.

Temporary or permanent discontinuation of study drugs: Certain events or conditions may necessitate temporary or permanent discontinuation of the study medication. Participants who experience such events or conditions, however, will still be "on study" and will be followed until study completion. Any participant for whom the study medication is temporarily discontinued will be restarted on study medication as soon as possible. Study regimens will be discontinued and non-study regimens will be used with continued study follow-up for participants who fail to respond to study therapy either clinically and/or bacteriologically, for participants in whom treatment-emergent drug toxicity warrants discontinuation of study therapy. If study drugs are permanently discontinued, further TB therapy will be administered at the investigator and treating clinicians' discretion.

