8.1.1 Liver toxicity

A liver toxicity management plan will be implemented if either of the criteria outlined below are met:

- ALT > 5x the upper limit of normal (ULN)
- ALT > 3x ULN with signs or symptoms suggestive of clinical hepatitis including one or more of the following: nausea, vomiting, abdominal pain, dark or clay colored stools, unexplained fever, jaundice, liver tenderness, or hepatomegaly

Management plan:

- 1. Discontinue pyrazinamide
- 2. Assess for use of other hepatotoxic drugs and discontinue potentially hepatotoxic, nonessential medications (e.g., co-trimoxazole, fluconazole)
- 3. Repeat ALT, bilirubin, and INR every 2 (+/-1) days
- 4. If the transaminases fall to <5x ULN and symptoms resolve, continue treatment without pyrazinamide.
- 5. If the transaminases do not fall to <5x ULN or bilirubin is >2.0 mg/dL or INR >1.5, or symptoms worsen, stop rifampicin and isoniazid, and start alternative regimen for TB meningitis (e.g., streptomycin and fluoroquinolone).
- 6. Continue to follow ALT every 2 (+/-1) days until stable. If the ALT return to <2x ULN and symptoms resolve, rifampicin will be restarted. If ALT remain stable after a minimum of 7 days, isoniazid will be restarted, and streptomycin and fluoroquinolone stopped.
- 7. Continue to follow ALT every 2 (+/-1) days until stable. If ALT begin to rise again to >5x ULN after reintroduction of either rifampicin or isoniazid, stop the offending medication. Depending on which medication has to be stopped (or potentially both), treat with 1) streptomycin, fluoroquinolone, and ethambutol OR 2) rifampicin, fluoroquinolone, and ethambutol OR 3) isoniazid, fluoroquinolone, and ethambutol.

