8.1.7 Criteria for temporary discontinuation of study therapy

- Development of a toxicity that, depending on its nature and severity, requires temporary discontinuation of the study medication until the toxicity resolves as indicated in the preceding toxicity management section.
- Development of another medical condition that makes the administration of the study drug inadvisable. The decision to discontinue temporarily the study medication in this situation will be at the investigator's discretion. The period during which the participant is off study medication will be as short as clinically possible.

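### For a liver event attributed to study rifampicin that is still Grade 4 on repeat, 8.1.1 restarts rifampicin and 8.1.6 stops it permanently; nothing says which governs

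*Combined protocol and SAP*

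**What the plan says.** Section 8.1.1 (Liver toxicity) starts when ALT exceeds 5x ULN, or 3x ULN with symptoms of hepatitis. It sets no upper grade limit. Step 1 stops pyrazinamide. Step 3 is "Repeat ALT, bilirubin, and INR every 2 (+/-1) days". Step 4 continues treatment without pyrazinamide if transaminases fall below 5x ULN and symptoms clear. Step 5 reads: "If the transaminases do not fall to <5x ULN or bilirubin is >2.0 mg/dL or INR >1.5, or symptoms worsen, stop rifampicin and isoniazid". Step 6 reads: "If the ALT return to <2x ULN and symptoms resolve, rifampicin will be restarted". No step mentions linezolid, and step 6 names no dose.

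Section 8.1.6 (Other toxicities) says of Grade 4 events: "Any participant with grade 4 renal, hepatic, cardiac, hematological, or neurologic toxicity will be immediately discontinued from study therapy". Items 1 and 2 deal with a repeat test of Grade 3 or lower. Item 3 deals with a repeat that is still Grade 4: "If the repeat test shows grade 4 toxicity, then the participant will be permanently discontinued from study medications". The exception is a clearly identified alternative cause, and re-administration then needs prior approval from the PI and the site PI. After a permanent stop, "Further treatment of TB will be directed by the investigator and treating clinician on an individualized basis".

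Sections 8.0 and 8.1 limit these rules to toxicity attributable to drugs that the study provides, and 8.1 names linezolid and rifampicin.

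**The concern.** A participant with Grade 4 ALT falls under both sections. Both use mandatory wording, and neither cross-refers to the other. If the event is attributed to study rifampicin and the repeat is still Grade 4, a site following 8.1.1 to its end would restart rifampicin once ALT settles, possibly at 35 mg/kg. A site following 8.1.6 would never give the study drug again. What is at stake is participant safety after a confirmed severe liver event, and consistent handling between participants.

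There is a lesser risk at the first Grade 4 result. Staff who open the liver section and go no further would stop pyrazinamide and might miss the immediate stop of study drugs that 8.1.6 requires.

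**Working it through.** No arithmetic applies, and the plan gives no figure to reproduce. The check sets the two sections side by side for one event: ALT-defined, Grade 4, attributed to study rifampicin.

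**Do both sections apply?** Section 7.2 adopts the DAIDS grading table, but the Grade 4 ALT cut-off is not printed. If it is at or above 5x ULN, every ALT-defined Grade 4 event also triggers 8.1.1. If it were between 3x and 5x ULN, events below 5x would trigger 8.1.1 only with symptoms. The first case is assumed here.

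| Stage | 8.1.1 | 8.1.6 | Can both be followed? |
|---|---|---|---|
| First Grade 4 result | Stop pyrazinamide; stop rifampicin and isoniazid if a step 5 criterion is met; silent on linezolid | Stop study therapy at once | Yes: stop pyrazinamide and the study drugs the same day |
| Repeat Grade 3 or lower | Continue without pyrazinamide, or step 5 and then step 6 | Item 1 (drugs continued): manage by the repeat grade. Item 2 (drugs held): re-administration at the investigator's discretion | Largely yes |
| Repeat still Grade 4, ALT later below 2x ULN, symptoms resolved | Rifampicin is restarted, no dose given | Study medications stopped permanently | Only if the restart means standard-dose rifampicin |

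**Does any text set precedence?**
- Section 8.1 allows one or more study medications to be held or stopped, but does not rank the subsections.
- Section 8.1.6 later states "Study regimens will be discontinued and non-study regimens will be used with continued study follow-up" for toxicity that warrants stopping. It does not mention 8.1.1.
- Section 8.1.7 defers to the toxicity section as a whole: "until the toxicity resolves as indicated in the preceding toxicity management section".
- Section 9.1 lists toxicity that requires a permanent stop, but does not say when a stop is required.

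**Which drug is in dispute?** Under 5.2 the study supplies the 300 mg rifampicin tablets and linezolid; the fixed-dose combination tablets come from routine care. By Table 4, only Arms A and C receive the additional rifampicin tablets. Standard-dose rifampicin can still be given after a permanent stop, because 8.1.6 leaves later TB treatment to the clinicians. The unresolved question is therefore whether step 6 may return a participant to the high dose. Under 5.1 everyone moves to standard therapy after week 4, so this matters mainly when ALT recovers within the four-week intervention period.

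**The case against.** The strongest defence is the heading of 8.1.6. *Other toxicities* follows dedicated subsections, so *hepatic* there could mean only liver events outside the ALT trigger, and 8.1.1 would then govern alone. That reading is possible, but the text does not establish it. 8.1.6 names hepatic, hematological and neurologic toxicity, all of which have their own subsections, and then gives a separate discretionary rule for remaining Grade 4 events. The named organs look like a deliberately stricter class.

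Other objections stand and limit the point:
- A reader might infer that the sections conflict from the first Grade 4 result. They do not. 8.1.1 does not forbid stopping study drugs early, and step 5 lets rifampicin stop on bilirubin, INR or worsening symptoms without waiting for a repeat ALT.
- A reader might infer that 8.1.1 keeps linezolid going. Silence is not an instruction to continue, and 8.1 and 9.1 both allow a stop.
- A reader might infer that *study therapy* is wholly open. Sections 7.3 and 8.1, and the Grade 3 paragraph of 8.1.6, all point to rifampicin and linezolid. Only the rifampicin inside the fixed-dose tablets remains unclear.
- The PI and site PI must be told within 24 hours of a toxicity that changes study treatment (8.0), and step 7 of 8.1.1 stops the offending drug if ALT rises above 5x ULN again. These reduce the risk, but neither says which rule applies.

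**Conclusion.** The point holds for one situation: Grade 4 ALT attributed to study rifampicin, still Grade 4 on repeat, with no clear alternative cause. There, two mandatory safety rules give different answers on returning to the study dose, and the protocol does not choose between them. It rests on the assumption that the Grade 4 cut-off is at or above 5x ULN.

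The reach is small. Section 1.0 regards isoniazid and pyrazinamide as the likelier causes of transaminase rises, and events attributed only to them are outside this point. The documents give no Grade 4 rates, so no count can be offered. A reader might extend the criticism to 8.1.2 and 8.1.4, but their restarts are permissive, so no incompatibility arises there. Nor do the documents support a claim that sample size or the primary PK analysis is affected. The change is still worth making, because it concerns re-exposure after a confirmed severe liver event.

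**What to change.** Add a Grade 4 step to 8.1.1 with three parts:
1. When Grade 4 ALT is attributed to a study drug, 8.1.6 applies first: linezolid and the additional 300 mg rifampicin tablets stop at once.
2. 8.1.1 then governs the backbone drugs.
3. If the repeat is still Grade 4, any restart under step 6 is standard-dose rifampicin only.

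In 8.1.6, state that study therapy means linezolid and the study-provided additional rifampicin.

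The cost is a wording amendment with IRB/ethics approval and a memo to site staff. Sample size, visits and data collection do not change.

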8.1.7 Criteria for temporary discontinuation of study therapy

- Development of a toxicity that, depending on its nature and severity, requires temporary discontinuation of the study medication until the toxicity resolves as indicated in the preceding toxicity management section.
- Development of another medical condition that makes the administration of the study drug inadvisable. The decision to discontinue temporarily the study medication in this situation will be at the investigator's discretion. The period during which the participant is off study medication will be as short as clinically possible.

8.2 Management of CNS tuberculomas

Participants with radiologic evidence of a CNS tuberculoma or other mass lesion on initial head CT or MRI are eligible for the study. Participants who develop a CT or MRI-confirmed CNS tuberculoma or other mass lesion after enrollment can remain on study treatment. In both circumstances, the duration of therapy and corticosteroids can be modified at the discretion of the investigator and treating clinician.

8.3 Management of Resistant TBM

Participants with known current or previous drug resistant TB infection will be excluded from the trial. If participants are determined to have resistant infection based on phenotypic testing after enrollment, they may discontinue study treatment at the discretion of the investigators and treating clinicians but will remain "on study" for follow up evaluations as per the schedule of events, including:

- Symptom assessment since last study visit.
- Targeted physical exam, including neurologic exam with GCS
- Medication review
- Adherence questionnaire, including documentation of all doses received
- Neuropathy and vision testing
- Neurocognitive and functional outcome assessment

8.4 Management of Participants with Suspicion of Relapse Post-treatment or New Neurological Event

All efforts should be made to complete the assessments listed below as soon as possible:

- Symptom assessment
- Targeted physical exam, including neurologic exam with GCS
- Medication review
- Adherence questionnaire, including documentation of all doses received
- Blood draw for a complete blood count and chemistries including LFTs if indicated
- Brain imaging if indicated
- CSF specimen for protein, cell count, differential, glucose, gram stain, bacterial culture, AFB smear and culture, and Xpert Ultra. Positive culture isolates will be sent for drug susceptibility testing for M. tuberculosis
- Whole blood and plasma collected for storage

8.5 Management of Pregnancy

If a participant becomes pregnant during the study, she will be discontinued from study medications and will continue treatment of her TB according to local standards of care, to a prenatal care program for management of her pregnancy according to local standards of care, and to their local HIV clinic. Participants who become pregnant during the study will be followed through the end of the study period. At the end of the pregnancy, the outcome and AEs for the participant and the infant will be recorded. If a participant has completed the study or chooses to discontinue from the study before the end of the pregnancy, then the study team should request permission to contact her regarding pregnancy outcomes at the end of pregnancy. If the information is obtained, pregnancy outcomes will be recorded at the end of the pregnancy.

All four first line antituberculous drugs have an excellent safety record in pregnancy and are not associated with human fetal malformations. The effects of higher dose rifampicin and linezolid on the developing human fetus are unknown. For this reason, women of childbearing potential must agree to use adequate barrier contraception or abstinence for the duration of study participation. Women of childbearing-potential will have a pregnancy test prior to enrollment. Should a woman become pregnant while participating in this study, she should inform study staff immediately. Female participants of "childbearing potential" are defined as women who have reached menarche or who have not been post-menopausal for at least 24 consecutive months or have not undergone surgical sterilization. Hormonal contraception is not recommended because it will not be effective due to induction of metabolism when receiving rifampicin. This information will be discussed with female participants when their mental status normalizes at the time they are re-consented.

8.6 Management of ART

During the trial HIV therapy will be provided in partnership with local HIV services through Masaka Regional Referral Hospital. For those participants already on effective first-line ART at presentation, it will be continued. In participants on a failing first-line ART-regimen, it will be switched after the intensive phase of TB treatment in accordance with local guidelines. Patients on a protease-inhibitor based regimen at presentation are not eligible to be enrolled into the trial due to the drug interactions.

9.0 CRITERIA FOR DISCONTINUATION

9.1 Permanent and Premature Treatment Discontinuation

- Drug toxicity that is possibly, probably or definitely related to high-dose rifampicin or linezolid, and that requires permanent discontinuation of any of these drugs
- Confirmed drug-resistant MTB infection
- Another infection cause found that is not MTB
- Sustained non-adherence that, in the opinion of the investigator, warrants early discontinuation.
- Requirement for prohibited concomitant medications.
- Pregnancy or breastfeeding.
- Request by participant or next of kin/caregiver to terminate treatment.
- Clinical reasons believed life threatening by the physician, even if not addressed in the toxicity section of the protocol

Participation is entirely voluntary so participants may choose to discontinue the trial treatment at any point without penalty. Participants should be encouraged to remain in the trial for the purpose of follow-up and data analysis. Where study drug is discontinued or the dose is modified it should be recorded in the follow-up CRF.

9.2 Premature Study Discontinuation

- Request of a medical provider or investigator if they think the study is no longer in the best interest of the participant.
- The participant or next of kin/caregiver refuses further follow-up evaluations (i.e., withdraws continued consent to participate).
- At the discretion of the IRB and other regulatory authorities as part of their duties to ensure that research participants are protected, or the industry supporter or its designee.

10.0 STATISTICAL CONSIDERATIONS

10.1 Sample size estimation

Sample size calculations for the PK analyses are based on different study designs (varying number of participants and time points) using clinical trial simulations. We used the stochastic simulationestimate "sse" methodology for clinical trial simulation and re-estimation to determine sample sizes required to evaluate key PK parameters with precision adequate to determine optimal dosing for a future efficacy trial of LZD. This methodology simulates the data from a planned trial with a proposed design (e.g., number of participants) followed by the estimation of the parameters under the true and alternative models. This is repeated a minimum of 1000 times to estimate PK parameters, standard errors and inter-individual variability. With 30 participants receiving LZD, we will be able to estimate PK parameters with required precision of relative standard errors <10% for typical values and <25% for random effects (inter-individual variability). For the evaluation of LZD adverse events, if we assume 40% of participants in the LZD arm and 10% in the no LZD arm will experience myelosuppression.^{78,84} the planned sample size of 60 participants (n=30 per arm) will provide at least 80% power to detect a similar or greater difference in the frequency of myelosuppression between arms at a significance level of 0.05. Given the modest sample size, we recognize that we may not have adequate power to compare the frequency of myelosuppression in participants on LZD and standard versus high dose RIF; however, if the frequency of myelosuppression in participants on LZD and high dose RIF (n=20) is anticipated as \sim 25%, the 90% confidence interval of this estimate is 10% to 46% with a precision of 18%.

